6.2 Schedule of Assessments and Risks

Screening/enrolment

Study name:	y name: Traumatic brain injury related changes in military veterans						
Protocol version number:	3.0	version date:	11 October 2023	Page:	15 of 22		

Patients' eligibility and willingness to participate will be assessed as described above in the section on consent.

Clinical assessments (Contact 1-6)

All participants recruited will undergo collection of blood and saliva to detect fluid biomarkers of injury, visual function assessments, mental health status and PROMs. Assessments at the 12 month point will be conducted face to face where possible, but where patients are unable to attend (e.g. have moved away) will be conducted remotely. Study time points for visits 2-6 will allow a 10% variation from stated timings. Face to face visits will therefore be at enrolment, 1 month (acute TBI only), 6 months (all patients) and 12 months (acute TBI and veterans where possible).

Taking blood using a needle is uncomfortable, can cause bruising and bleeding and sometimes fainting. Only trained staff will collect the blood samples to ensure this does not occur. Saliva will be collected in a tube and is not invasive and should not cause any problems.

Visual function tests: visual acuity measurements with normal refractive correction and pinhole where vision is less than logMAR 0 monocularly; colour vision assessed monocularly using Colour Assessment and Diagnosis (CAD); visual field assessed using the SITA Fast 24-2 Humphrey Visual Field-testing algorithm, contrast sensitivity test by monocular reading Pelli-Robson contrast chart or Acuity Plus (on the CAD), pupil assessment using a pupillometer and visual focussing mechanism and ocular motility are assessed using autorefraction and Email saccadic latency assessment respectively. OCT will be used to image the retina and optic nerve head. Dilating drops (tropicamide 0.5%) may be applied where necessary to assist the assessment where this would not interfere with assessment by the neurosurgical team (e.g. when an inpatient on neuroobs). All visual function assessments and OCT imaging will be carried out at contact points 1 and 3 and where possible at close out (contact 6) when the patient is able to cooperate, although all subjective assessments may not be possible in the acute phase after TBI. Additionally, head injury outcome (i.e. Glasgow outcome scale (daily living assessment by a physician); Mayo-Portland Adaptability Inventory (physical and daily living assessment by a physician) will be assessed at the final visit as part of routine care. There are no risks associated with these tests as they are an assessment of patient's abilities by a physician.

We will use eye drops as per standard care to dilate patient eyes, as is routine. This may mean that patient eyes will be more sensitive to light and can take up to 6 hours to become normal. We will recommend the use of sunglasses to minimise the impact of light to patient eyes. We will also recommend that patients do not drive and that someone accompanies them. We will refund travel expenses.

Mental health status and self-reported measures (PROMs): Clinician-led completion of the social and occupational functioning assessment scale (SOFAS) will be completed at each Outpatients visit. Self-reported PROMs using cross-cutting questionnaires will assess a range of outcomes such as Brain Injury Vision Symptom Survey (BIVSS for visual impairment), Patient Health Questionnaire (PHQ-9 for depression), General Anxiety Disorder (GAD-7 for anxiety), PTSD Checklist for DSM-5 (PCL-5 for PTSD), Suicidal Behaviour Questionnaire Revised (SBQ-R for suicide ideation), Alcohol Use Disorders Identification Test (AUDIT) and quality of life (EQ5D5L for alcohol abuse). All of these questionnaires are validated and widely used. These PROMs will be completed in paper format remotely and posted to the research team in stamped addressed envelopes which will be provided to each participant.

During the study, it may be that a diagnosis of psychiatric problems is found. If so, we will refer the patient to the care team for further support. We will also provide details of local voluntary organisations that can help. If a patient self-reports any suicidal thoughts or behaviours, they will be contacted by the care team to provide further support. In addition, we will provide details of dedicated organisations such as Samaritans, Campaign against living miserably (CALM), Papyrus, Childline or SOS Silence of Suicide. We will also direct them to contact someone they trust, their GP, call 111 or their mental health crisis team (if they have one) to talk over their issues.

Study name:	Traumatic brain injury related changes in military veterans						
Protocol version number:	3.0	version date:	11 October 2023	Page:	16 of 22		

7. Adverse Event Reporting

All investigations are routine clinical investigations or variants thereof that normally do not carry any appreciable risks of adverse events (AEs). The collection and reporting of AEs, however, will be in accordance with the UK Policy Framework for Health and Social Care Research and the requirements of the National Research Ethics Service (NRES) and Health Research Authority (HRA). Definitions of different types of AEs are listed in the table of abbreviations and definitions. The Investigator should assess the seriousness and causality (relatedness) of all AEs experienced by the study participant this should be documented in the source data with reference to the protocol. We will also follow University of Birmingham processes for safety reporting as per the Quality Management System: https://www.birmingham.ac.uk/research/activity/mds/mds-rkto/governance/qms.aspx.

8. Samples

Blood (7ml) and saliva (2-3ml) will be collected in standard tubes in the outpatients department of UHB and these volumes are routinely collected as part of standard care. Blood will be collected by the clinical care team by trained nurses/doctors. Saliva is collected by simply spitting into a special tube containing a stabiliser reagent. Needlestick injuries during blood collection are minimised by trained and competent nurses/doctors who will collect blood.

All samples will be transported by the research team and stored in labelled aliquots and in lockable, HTA compliant freezers. Samples will be transported to University of Birmingham labs and rendered acellular by centrifugation. Serum and saliva samples will then be aliquoted and stored in lockable freezers until required. Biomarkers will be detected in serum and saliva by enzyme linked immunosorbent assays (ELISA) using commercially available kits. See attached risk assessment form (COSHH human biological fluids).

After analysis, any remaining samples will be kept in locked University-owned freezers for up to 10 years or transferred to other ethically approved projects looking at serum and saliva biomarkers.

9. Data Handling and Record Keeping

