1.2.2. Justification for design

This is a prospective observational pilot study. Following 3 groups of participants, including an acute TBI group, a veterans' group with diagnosed TBI and a control group with no previous episodes of brain injury allows us to: (a) assess the changes in fluid and imaging biomarkers and (b) assess mental health status and quality of life over time. Values obtained from levels of biomarkers and measures for mental health status and quality of life will be subtracted from data in the acute TBI and the veteran group. This will reveal changes over time in acute TBI patients who have suffered a TBI and in veterans with TBI. Comparisons between the acute TBI group and the veteran group will then reveal differences between these two groups and whether one group is more susceptible to worse mental health and quality of life status. Since, we will collect longitudinal data, we may be able to tell how long after a TBI do the reported mental health and quality of life problems occur in acute TBI and veterans with a view to developing therapeutic intervention to delay or treat these problems.

We will compare these with the same biomarkers and assessments in control patients (without any episodes of brain injury). This will help us to understand if there is anything different in TBI patients that may tell us who is likely to go onto to develop mental health problems and poorer quality of life outcomes.

Whilst we will aim to perform all investigations at all time points on all patients, not all patients will be able to devote sufficient time and effort to participate and, as this is an exploratory study, we will not exclude patients where they fail to complete all stages of the assessment.

2. Aims, Objectives and Outcome Measures

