6.1. Summary of assessments

Figure 2. Assessments planned for acute TBI patients

		TRI	AL PERIOD	
	Enrolment	Initial assessment (may be at enrolment)	Post-allocation (monitoring interval clinically determined)	Close-out
TIMEPOINT**	-t1	Contact 1 (0-14 days post head injury or at enrolment)	Contact 2-5 (1, 3, 6 and 9 months after head injury or enrolment)	Contact 6 (12 months after head injury)
ENROLMENT:				
Eligibility screen	Х			
Informed consent	Х			
ASSESSMENTS:				
Collect blood and saliva		X (face to face)	X (1 and 6 months only, face to face)	X (face to face)
Visual function tests (e.g. visual acuity and field tests, optical coherence tomography (OCT), OCT angiography, pupillometry, Email saccadic latency and autorefraction.		X (face to face)	X (1 and 6 months only, face to face)	X (face to face)
Mental health outcomes (social and occupational functioning assessment)		X (face to face and remotely)	X (1 and 6 months only, face to face and remotely)	X (face to face or remotely)
Self-reported measures collected by post (e.g. BIVSS (visual impairment, General anxiety disorder, PTSD, Suicidal behaviour, alcohol use and quality of life		X (all collected remotely)	X (1, 3, 6 and 9 months, all collected remotely)	X (all collected remotely)
Head injury outcome				х

Study name:	Fraumatic brain injury related changes in military veterans					
Protocol version number:	3.0	version date:	11 October 2023	Page:	13 of 22	

		TRI	AL PERIOD	
	Enrolment	Initial assessment (may be at enrolment)	Post-allocation (monitoring interval clinically determined)	Close-out
TIMEPOINT**	- t 1	Contact 1 (at enrolment)	Contact 2-4 (3, 6 and 9 months enrolment)	Contact 5 (12 months after enrolment)
ENROLMENT:				
Eligibility screen	Х			
Informed consent	Х			
ASSESSMENTS:				
Collect blood and saliva		X (face to face)	X (at 6 months only, face to face)	X (face to face)
Visual function tests (e.g. visual acuity and field tests, optical coherence tomography (OCT), OCT angiography, pupillometry, Email saccadic latency and autorefraction.		X (face to face)	X (at 6 months only, face to face)	X (face to face)
Mental health outcomes (social and occupational functioning assessment)		X (face to face and remotely)	X (at 6 months only, face to face or remotely)	X face to face or remotely)

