Self-reported measures collected by post (e.g. BIVSS (visual impairment, General anxiety disorder, PTSD, Suicidal behaviour, alcohol use and quality of life		X (all collected remotely)	X (at 3, 6 and 9 months, all collected remotely)	X (all collected remotely
Head injury outcome				Х

Figure 3. Assessments planned for military veterans group

Study name:	Traumatic brain injury related changes in military veterans					
Protocol version number:	3.0	version date:	11 October 2023	Page:	14 of 22	

-igure 4. Assessments pl		,,,,,,,,,,,,,,,,,,,,,,,,,,,,,,,,,,,,,,,	AL PERIOD	
	Enrolment	Initial assessment (may be at enrolment)	Post-allocation	
TIMEPOINT**		Contact 1 (single assessment point)	Contact 2 (6 months after enrolment)	
ENROLMENT:				
Eligibility screen		Х		
Informed consent		Х		
ASSESSMENTS:				
Collect blood and saliva		X (face to face)	X (face to face)	
Visual function tests (e.g. visual acuity and field tests, optical coherence tomography (OCT), OCT angiography, pupillometry, Email saccadic latency and autorefraction		X (face to face)	X (face to face)	
Mental health outcomes (social and occupational functioning assessment)		X (face to face and remotely)	X (face to face or remotely)	
Self-reported measures collected by post (e.g. BIVSS (visual impairment, General anxiety disorder, PTSD, Suicidal behaviour, alcohol use and quality of life		X (all collected remotely)	X (6 months, all collected remotely)	
Head injury outcome		N/A		

Figure 4. Assessments planned for non-head injury control group

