12.2. Power Calculation and Statistical Analysis

Data obtained from all clinical examinations and laboratory tests will be compared between the first visit (Contact 1) and the subsequent follow-up visits (Contact 2-6). Many of these data are continuous and normally distributed as well as being repeated measures data of the same subjects. As such, repeated measures ANOVA will be used to determine changes over time. Data that are not normally distributed or numeric will be analysed using non-parametric tests. Linear mixed models, linear regression and analysis of covariance will be used for binary and ordinal outcomes as appropriate. Trial statisticians in the Birmingham Clinical Trials Team will be engaged for further statistical advice, if required.

This is a pilot study to evaluate longitudinal changes in fluid and visual biomarkers of brain injury, mental health status and self-reported quality of life measures in patients with TBI (civilian and military veterans). The sample size is based on:

1) statistical advice that in a pilot / feasibility study, 30 subjects in each group are recommended to allow estimation of the parameters of interest³².

2) Based on Child's et al.³² which showed a difference of 5um in global retinal nerve fibre layer thickness between boxers and controls, an average RNFL thickness of 101. Past experience in the concussion clinic suggests that we are able to follow 80% of patients at the 3-month point (i.e. only 20% lost to follow up). We based the power calculation looking for power to detect a 5um change in the repeated measures, assuming correlation of 0.9 between repeated measures of RNFL thickness (conservative given that in the absence of pathology, RNFL thickness varies very little). Simulated power calculations in R revealed that 24 participants with complete data (recruiting 30 and assuming a 20% drop out) would have >80% power to detect a 2µm change in RNFL thickness and 100% power to detect a 5µm decrease.

13. Ethical Considerations

The study will be performed in accordance with the recommendations guiding physicians in biomedical research involving human subjects, adopted by the 18th World Medical Association General Assembly, Helsinki, Finland, June 1964, amended at the 48th World Medical Association General Assembly, Somerset West, Republic of South Africa, October 1996 (website: http://www.wma.net/en/30publications/10policies/b3/index.html).

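### Section 6.2 schedules OCT and visual tests by contact number, but those numbers mean different months in each group; taken literally, the sentence contradicts Figures 2–4 and drops the acute group's 6-month scan

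*Protocol*

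**What the plan says.** The Protocol gives the visual and OCT schedule in three places.

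- **Section 6.2, visual function paragraph.** The visual tests and "OCT imaging will be carried out at contact points 1 and 3 and where possible at close out (contact 6". No group is named and no month is given.
- **Section 6.1, Figures 2–4.** For acute TBI, Figure 2 has "Contact 2-5 (1, 3, 6 and 9 months after head injury or enrolment" and then "Contact 6 (12 months after head injury". Its visual-test row between the first contact and close-out reads "X (1 and 6 months only, face to face". Figure 3 gives veterans contacts 2–4 at 3, 6 and 9 months and close-out as contact 5 at 12 months, with visual tests at enrolment, 6 and 12 months. Figure 4 gives controls a first contact and "Contact 2 (6 months after enrolment", with visual tests at both.
- **Section 6.2, clinical assessments paragraph.** Face-to-face visits are listed by month: enrolment, 1 month for acute TBI only, 6 months for everyone, and 12 months for the two TBI groups where possible.

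The analysis text uses contact numbers too. In section 12.2, examination and laboratory data "will be compared between the first visit (Contact 1) and the subsequent follow-up visits (Contact 2-6".

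**The concern.** A contact number identifies a time point only if it means the same thing in every group, and after contact 1 these numbers do not. A site following the visual function paragraph and a site following Figure 2 would scan acute participants in different months.

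A missed scan cannot be recovered at analysis, so this is more than a matter for the statistical analysis plan. The scan most exposed is the acute 6-month one, in the only follow-up month when controls are also scanned. OCT is not incidental either: the second justification for the sample size in section 12.2 rests on retinal nerve fibre layer thickness in repeated measurements.

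**Working it through.** The Protocol states no figure on this point to reproduce. The check is a mapping of the schedules, with contact 1 taken as month 0 in every group (for acute participants it may fall 0–14 days after injury).

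**Step 1. Month of each contact, from Figures 2–4.**

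| Contact | Acute TBI | Veterans | Controls |
|---|---|---|---|
| 1 | 0 | 0 | 0 |
| 2 | 1 | 3 | 6 |
| 3 | 3 | 6 | none |
| 4 | 6 | 9 | none |
| 5 | 9 | 12 | none |
| 6 | 12 | none | none |

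Only contact 1 is common to all three groups.

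**Step 2. OCT months: contacts 1, 3 and 6 taken literally, against the figures.**

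| Group | Literal 6.2 | Figure | Missed | Added |
|---|---|---|---|---|
| Acute TBI | 0, 3, 12 | 0, 1, 6, 12 | 1, 6 | 3 |
| Veterans | 0, 6 | 0, 6, 12 | 12 | – |
| Controls | 0 | 0, 6 | 6 | – |

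The figures hold 4 + 3 + 2 = 9 scan occasions. The literal reading misses 2 + 1 + 1 = 4 of them and adds 1. If the word for close-out is allowed to override the contact number for veterans, 3 are missed. The sentence fits no group's table: contact 6 as close-out is true only of acute participants, and a scan at contact 3 is true only of veterans.

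**Step 3. Can the visit window absorb the conflict?** Section 6.2 allows 10% either side of the stated time. That gives 0.9–1.1 months for the 1-month visit, 2.7–3.3 for 3 months and 5.4–6.6 for 6 months. The intervals do not overlap, so a 3-month scan cannot stand in for either of the others.

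**Step 4. Comparisons with controls.** By the figures, the OCT months common to all groups are {0, 1, 6, 12} ∩ {0, 6, 12} ∩ {0, 6} = {0, 6}. If the literal rule is applied to acute participants and Figure 4 to controls, acute and controls share {0, 3, 12} ∩ {0, 6} = {0}, which is baseline only; veterans and controls still share {0, 6}. If the literal rule is applied to controls as well, they have no follow-up scan and neither TBI group has a controlled change.

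**Step 5. Section 12.2.** Contacts 2–6 are five follow-ups in the acute group. Veterans have four (contacts 2–5) and controls one (contact 2). Matched by month, controls have a value at month 6 only:

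| Follow-ups with a control value in the same month | Acute TBI | Veterans |
|---|---|---|
| Self-reported measures (acute: "X (1, 3, 6 and 9 months, all collected remotely" and close-out) | 1 of 5 | 1 of 4 |
| Blood, saliva, visual tests, SOFAS | 1 of 3 | 1 of 2 |

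**The case against.** **It is one stray sentence.** Three figures and the face-to-face list, which is itself in section 6.2, agree on a schedule in months. That is right, and it makes the authors' intention easier to guess. It does not remove the conflict, because the sentence sets out all the visual testing and cannot be matched to any one figure. Counting only face-to-face visits does not rescue it: the third such visit for an acute participant is indeed at 6 months, but close-out would then be the fourth, not the sixth, and the 1-month scan would still be missing.

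**Visual function is a secondary outcome in an exploratory pilot, and few control visits are a design choice.** Both stand. The point is not that controls need more visits. It is that the schedule should be unambiguous and its limits stated.

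**Section 12.2 describes change within the same participants.** This also stands. A reader might infer that groups are to be lined up by contact number, so that 1-month acute data are set against 3-month veteran and 6-month control data. No passage says so. What remains is that the stated range of contacts exists only in the acute group.

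**Section 1.2.2 and subtraction.** A reader might take the statement that values of biomarkers and "measures for mental health status and quality of life will be subtracted from data in the acute TBI and the veteran group" to mean that a control mean is subtracted at each contact and treated as known, giving standard errors that are too small and too many false positives. The text does not support this. It does not name the source of the subtracted values, the time point, or any test that treats them as fixed. A single common constant would cancel from within-person change and from the acute-versus-veteran difference. Comparison with controls is described separately.

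**Conclusion.** The schedule is wrong as written and should be corrected before visits are booked from it. The visual function paragraph of section 6.2 contradicts Figures 2–4 and the face-to-face list in its own section. Taken literally, it misses four of nine planned scan occasions (three if close-out overrides the contact number for veterans) and adds one at a month with no planned visit. The main loss would be the acute-versus-control comparison of visual change to 6 months.

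A reader might conclude that the only controlled visual comparison disappears. It does not: all three groups are scanned at baseline, and the veteran-versus-control comparison at 6 months survives if controls follow Figure 4.

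Nor do controls lack a matching value at most time points for every measure. Counting baseline, the face-to-face measures lack one at 2 of 4 acute and 1 of 3 veteran time points. The shortfall is larger for the self-reported measures, at 4 of 6 and 3 of 5.

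The conclusion assumes only that contact numbers carry the meaning Figures 2–4 give them. The documents do not show which schedule sites actually follow.

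**What to change.** - Reconcile the visual function paragraph of section 6.2 with Figures 2–4 and the face-to-face list. Which months carry OCT in each group is for the investigators to settle.
- State every assessment in months, by group, and stop using contact numbers as time points. At the same time, correct the Figure 4 label that calls the control group's first contact its single assessment although a second follows.
- In section 12.2, index the comparisons by month within each group instead of by contacts 2–6.
- In sections 1.2.2 and 12.2, state that change over time can be compared with controls only from enrolment to 6 months, using the controls' own measurements, and that acute and veteran changes at other months are uncontrolled.

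The cost is rewording in sections 1.2.2, 6.1, 6.2 and 12.2, with no visits beyond those in the figures if the figures are kept. The price in interpretation is that the 12-month changes are openly described as having no control comparison, which is already true of the design.

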9.1. Source Data

In order to allow for the accurate reconstruction of the trial and clinical management of the subject, source data will be accessible and maintained.

All data should be recorded on and linked to electronic clinical record systems where possible. In addition, an electronic record of recruited patients, visits and tests performed and, where possible, results with dates will be kept in the site file.

